6.6.3 Time-to-Event Analyses

Kaplan-Meier methods will be used to estimate cumulative probabilities and quartiles (25th percentile, median, and 75th percentile) of time-to-event endpoints (DoR, PFS, irPFS, and OS). The method of Brookmeyer and Crowley (1) will be used to construct two-sided 95% CIs around the quartile estimates. These calculations will be performed for all patients in cohort expansion by tumor type. Additional analysis may be carried out, by tumor type, on patients in the dose escalation cohort combined with those in the expansion cohort.

DoR will be calculated from the time of initial response (CR or PR) documentation (in patients who have a subsequent confirmation of objective response) to the time of progressive disease or death, whichever occurs first. Patients with CR or PR at time of last assessment will be censored at the time of their last tumor assessment. DoR will be calculated as follows:

DoR (months) = (progression date or death date or date of last tumor assessment – date of initial response+1) / (365.25/12)

PFS is defined as the time from first dose of study drug until documented disease progression or death from any cause, or date of last tumor assessment. A patient will be censored at the time of last assessment if the patient remains progression free at that time. Progression will be assessed using both RECIST 1.1 and irRC. PFS will be calculated as follows:

PFS (months) = (date of progression or date of death or date of last tumor assessment – date of first dose+1) / (365.25/12)

Overall survival (OS) is calculated from the time of first dose until death from any cause. Patients alive at study completion will be censored for analysis purposes. OS will be calculated as follows:

$$\text{OS (months)} = (\text{date of last contact or death date} - \text{date of first dose} + 1) / (365.25/12)$$

6.7 Safety Endpoint Analyses

6.7.1 Adverse Events

As mentioned in [Section 5.2](#), only TEAEs will be summarized in tables.

The following summaries of adverse event data will be created:

- All AEs
- Drug related AEs
- AEs by CTCAE Grade
- Drug related AEs by CTCAE Grade
- AEs with CTCAE Grade severity Grade ≥ 3
- All drug related AEs by CTCAE Grade severity Grade ≥ 3
- All SAEs (this may be a listing if there are few events)
- Drug related SAEs
- Fatal AEs (this may be a listing if there are few events)
- Adverse events of special interest (AESIs)
- AEs that result in study discontinuation
- AEs which lead to dose interruption
- AEs that lead to withdrawal of study drug

All of these summaries will display the number and percent of patients that experience the given event and will display events by System Organ Class (SOC) and Preferred Term (PT) from the MedDRA dictionary. Events will be displayed in alphabetically for SOC incidence and in descending order of overall PT incidence within each SOC.

An overall summary of AEs will display the number and percent of patient/patients who experience at least one event of each of the following types:

- All AEs
- Drug Related AEs

- AEs with CTCAE severity \geq Grade 3
- Drug-related AE with CTCAE severity Grade \geq 3
- AEs by CTCAE Grade
- Drug related AEs by CTCAE Grade
- All SAEs
- Drug-related SAEs
- AEs that lead to dose interruption
- AE that results in study discontinuation
- AE that results in study drug withdrawal
- Fatal AEs
- AESIs

6.7.2 Laboratory Values

Summaries of laboratory values will display descriptive statistics for numerically quantified labs. Absolute values and changes from baseline will be summarized and grouped by lab panel (e.g., hematology, blood chemistry, and urinalysis). For each panel, the data will be displayed by lab parameter and visit. Shift tables may be generated.

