4.2.1 Hematologic Dose Limiting Toxicity

Hematologic DLT will be defined as follows:

- Grade 4 neutropenia lasting > 5 days
- \geq Grade 3 febrile neutropenia lasting > 48 hours or any \geq Grade 3 febrile neutropenia associated with hemodynamic compromise or objective evidence of infection
- Grade 4 thrombocytopenia, irrespective of duration
- Grade 3 thrombocytopenia associated with clinically significant bleeding
- \geq Grade 3 hemolysis

The following events will be specifically **excluded** from the definition of hematologic DLT

- \geq Grade 3 lymphopenia
- Grade 3 anemia that is not associated with other clinically significant complications

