4.5.1 Dose Delays

Patients who experience toxicity that is potentially dose-limiting should have study drug held pending assessment, management and resolution of the toxicity. For patients in whom the toxicity is assessed to be unrelated to study drug or for whom the toxicity does not meet the criteria for DLT, therapy may be re-instituted at the same dose and schedule that was administered prior to the event, presuming the toxicity has resolved to \leq Grade 1 in severity. Reinstitution of therapy shall be conducted as follows:

For patients in whom the toxicity is assessed to be related to study drug, dose interruptions of up to 14 days are allowed for drug related toxicity. This may include up to one missed dose of pembrolizumab and up to 2 consecutively missed doses of MGA271. For the MGA271+MGA012 combination, Cohort 4, this would allow for a maximum of one dose each of MGA271 and MGA012. The procedures at the original scheduled missed visit should be performed as soon as possible with treatment reinstated as if no delay had occurred, picking up at the day where the interruption occurred, and patients receive the full complement of pembrolizumab and MGA271 or MGA271+MGA012 or as outlined in The Time and Event Schedule ([Appendix 1](#)). Patients with infusion delays $>$ 14 days due to drug related toxicity will discontinue both study drugs, complete the End of Treatment visit, and then enter the Efficacy Follow-up Period.

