- Progression of the underlying neoplasm resulting in hospitalization or death (e.g., patient hospitalized for or dies from progressive disease [PD] only, without any other SAE) will be documented as an antitumor activity outcome and not as an SAE. If an SAE occurs in a patient and it is unclear whether the event is related to PD, the SAE should be reported.
- The reporting of laboratory/vital signs abnormalities as both laboratory findings and AEs should be avoided. They should not be reported as AEs unless any one of the following are met:
 - Any criterion for an SAE is fulfilled

- The laboratory/vital signs abnormality causes the patient to discontinue from the study treatment
- The laboratory/vital signs abnormality causes the patient to interrupt the study treatment
- The laboratory/vital signs abnormality causes the patient to modify the dose of study treatment
- The laboratory/vital signs abnormality requires intervention

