Clinical Laboratory Changes: Safety laboratory assessments will be carried out locally and evaluated by the Investigator to ensure patient safety. The Investigator is responsible for reviewing the results of all laboratory tests as they become available. Laboratory tests will be graded according to CTCAE v 4.03. Laboratory values that fall outside of a clinically accepted reference range or values that differ significantly from previous values must be evaluated by the Investigator for clinical significance. The Investigator may repeat the laboratory test or request additional tests to verify the results of the original laboratory tests. If the Investigator determines the laboratory value is an abnormal change from baseline and is of clinical significance for that patient, it is considered an AE. Generally, Grade 1 laboratory findings need not be reported as AEs unless clinically significant. The Investigator will evaluate laboratory findings of \geq Grade 2 or higher classification to determine their clinical significance and if an AE has occurred. Consistent with the CTCAE designation of Grade 3 events as severe or medically significant and Grade 4 events as life-threatening, Grade 3 and Grade 4 laboratory findings should be reported as AEs or SAEs, as appropriate. Grade 2 laboratory findings may be reported as AEs if, in the opinion of the Investigator, the event exhibits clinical significance. If clinically relevant abnormal laboratory values are associated with clinical symptom(s), or consistent with a diagnosis, the diagnosis should be reported as the AE (e.g., hemoglobin 9 g/dL in an adult female = anemia). If these clinically relevant abnormal laboratory values do not result in a diagnosis, the test result or finding should be reported as the AE assuming that it does not represent a laboratory error. Repeat testing may be indicated. Such laboratory values should generally be recorded as “increased” or “decreased” (e.g., change from baseline hemoglobin of 13 g/dL to 11 g/dL = hemoglobin decreased).

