9.4.2 Laboratory Values

Summaries of laboratory values will display descriptive statistics for numerically quantified labs. Summaries will be grouped by laboratory panel (e.g., hematology, blood chemistry, and urinalysis) and will be displayed by visit for each laboratory parameter.

A list of repeated labs including original values and repeat values will be included.

Graphs of mean values over time may also be generated.

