6 STATISTICAL METHODOLOGY

6.1 General Considerations

Summary statistics will consist of absolute and relative frequencies of each category of discrete variables and of means, standard deviations, medians, minimum and maximum values for continuous variables. Categorical data will be summarized by the number and percent of subjects falling within each category. Continuous variables will be summarized by descriptive statistics, including the mean, standard deviation, median, minimum, and maximum. Time-to-event endpoints will be summarized with median durations and corresponding 95% confidence intervals.

For change from baseline calculations, baseline is defined as the most recent value prior to the first infusion of any of the study drugs among MGA271, pembrolizumab or MGA012.

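### SAP 6.7.2 commits to no worst-grade laboratory table, so patient counts rest on AE reporting, where two rules disagree on Grade 3/4 findings that prompt no action

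*SAP*

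**What the plan says.** **Laboratory output.** SAP 6.7.2 summarizes absolute values and changes from baseline: "For each panel, the data will be displayed by lab parameter and visit. Shift tables may be generated". SAP 6.1 defines the statistics: "Continuous variables will be summarized by descriptive statistics, including the mean, standard deviation, median, minimum, and maximum". Protocol 9.4.2 adds one listing, "A list of repeated labs including original values and repeat values will be included", and optional graphs of means. Neighbouring sections go further. SAP 6.7.3 commits to counting patients by a QTcF threshold, and SAP 6.7.4 commits to vital-sign shift tables.

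**When a laboratory finding becomes an AE.** Protocol 7.8.1, repeated in the synopsis, discourages recording an abnormality both as a laboratory finding and as an AE: "They should not be reported as AEs unless any one of the following are met". The conditions are an SAE criterion, discontinuation, interruption, dose modification or a need for intervention. Protocol 7.8.6 says instead that "Grade 3 and Grade 4 laboratory findings should be reported as AEs or SAEs, as appropriate", and SAP 5.2.2 repeats this.

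**Potential Hy's law.** It is a DLT criterion (Protocol 4.2.3) and an immediately reportable event (Protocol 7.8.2.6). SAP 6.7 names no table of DLTs, immediately reportable events or Hy's law cases.

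**The concern.** Characterizing safety is the primary objective, and for laboratory toxicity the basic quantity is the number of patients who reached a given grade. No committed laboratory table gives it, so the AE tables of SAP 6.7.1 must. Those tables depend on what sites enter, and for one class of finding the sites have two instructions with opposite answers.

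Under Protocol 7.8.1 the laboratory output is where unactioned findings belong, yet that output does not count them. At stake is whether the reported number of patients with, for example, Grade 3 or higher lymphopenia reflects the patients or a site's reading of the protocol. A labelled count of potential Hy's law patients is also absent, although the data for both counts are already collected.

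**Working it through.** No figure in the plan is in dispute. The check sets the rules side by side and then asks whether the committed rows could recover the count.

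**1. What reaches the AE tables under either rule**
- Protocol 4.5.1: "Patients who experience toxicity that is potentially dose-limiting should have study drug held pending assessment, management and resolution of the toxicity".
- Protocol 6.5.2.2 holds drug for Grade 2 transaminases or bilirubin. It stops drug at Grade 3, with a separate threshold for patients with liver metastases and Grade 2 transaminases at baseline.
- A hold meets a Protocol 7.8.1 condition: "The laboratory/vital signs abnormality causes the patient to interrupt the study treatment".

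Most Grade 2 or higher liver findings, and many Grade 3 lipase findings, are therefore AEs under both rules.

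**2. What does not**
Protocol 4.2.1 excludes from DLT anything at or above "Grade 3 lymphopenia", so the 4.5.1 hold does not apply, and Protocol 6.5.2 has no rule for it. With no action and no SAE criterion:

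| Rule | Unactioned Grade 3/4 value is an AE? |
|---|---|
| Protocol 7.8.1 | No |
| Protocol 7.8.6, SAP 5.2.2 | Yes |

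A lipase elevation that resolves before the next dose is similar.

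**3. Can the by-visit rows supply the count?**
Assumed: n = 15 (maximum Cohort 4 size); 4 post-baseline visits; lymphocytes 1.5 x10^9/L in everyone at baseline; one value of 0.4 at each visit; Grade 3 or higher taken as below 0.5. With one outlying value among n, SD = |difference|/√n.
- Mean = (14 × 1.5 + 0.4)/15 = 1.43
- SD = 1.1/√15 = 0.28
- Median 1.5, minimum 0.4, maximum 1.5
- Change from baseline: mean −1.1/15 = −0.07, SD 0.28, median 0, minimum −1.1, maximum 0

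Every visit row is the same in both of these cases:
- same patient each visit: 1/15 = 6.7% ever Grade 3 or higher (exact 95% CI 0.2–31.9%)
- different patient each visit: 4/15 = 26.7% (7.8–55.1%)

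**4. Does the finding occur in this trial?**
Protocol 2.3.1.1.2 reports related lymphocyte count decreased in 5.3% of 133. Only 7/133 = 5.26% rounds to that (exact 95% CI 2.1–10.5%). The term is absent from the related Grade 3 or higher events listed at 5% or more, so at most 6/133 = 4.5% had it reported at that grade. The number of patients with Grade 3 or higher values is not given, so the number unreported cannot be estimated.

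**5. Concurrent liver values**
Assumed, in x ULN, at one visit with n = 15: ALT 4.0 in one patient and 0.6 in 14; bilirubin 2.5 in one patient and 0.5 in 14.
- ALT: mean (14 × 0.6 + 4.0)/15 = 0.83, SD 3.4/√15 = 0.88, maximum 4.0
- Bilirubin: mean (14 × 0.5 + 2.5)/15 = 0.63, SD 2.0/√15 = 0.52, maximum 2.5

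These rows are the same for one patient with both elevations or two patients with one each. By the grading in Protocol 6.5.2.2, ALT 4.0 is Grade 2 and bilirubin 2.5 is below Grade 3. Recorded as separate laboratory terms, such a case is therefore outside the Grade 3 or higher AE table.

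**The case against.** The strongest objection is that little is lost. The SAP states one rule only, that Grade 3/4 findings are AEs. It matches Protocol 7.8.6, the section devoted to AE reporting, and AE tables by CTCAE grade are committed. Lymphocyte count decreased and Grade 3 or higher lipase increased (6.0%, 8/133) were in fact reported as AEs. The numerical examples are constructed and show a general property of by-visit summaries. Table shells sit in a separate programming plan that is not available, and the tables could be produced later without being promised now.

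Much of this stands. It limits the problem to unactioned findings, and it rules out the inference that this trial has under-reported Grade 3/4 laboratory toxicity, which the documents do not show. It does not remove the conflict, because sites follow the protocol, which carries both rules. SAP 7 says the shells are based on the analyses in the SAP, so the programming plan cannot be assumed to add a commitment.

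A reader might also infer that Hy's law cases would be missed or hidden. The documents do not support that:
- Cases are DLTs and are reported within 24 hours. If drug-related as a DLT, they end all study treatment (Protocol 4.5).
- Protocol 7.8.6 and SAP 5.2.2 direct that a diagnosis replace its component laboratory terms, so a case may appear as one hepatic term.
- A case may also enter the AESI table. Protocol 7.8.3 limits immune-related AESIs to Grade 3 or greater, but Protocol 6.5.2 lists autoimmune hepatitis without a grade limit and 7.8.2.6 lists irAEs the same way.

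What is missing is a labelled count, not detection or patient protection.

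**Conclusion.** The point holds in a limited form. Committed laboratory output cannot give the number of patients by worst grade. For Grade 3/4 findings that prompt no action, the AE count depends on which of two conflicting rules a site followed. Its size in this trial is unknown. The 1/15 versus 4/15 contrast shows only that by-visit rows cannot settle the matter, and it rests on the assumed values above. Most Grade 2 or higher liver findings are captured through holds, so the conflict does not extend to laboratory toxicity in general. For potential Hy's law the gap is one of tabulation: no committed table states how many patients met the criteria. This is worth correcting because it concerns the primary objective and the remedy is cheap, but it does not threaten the trial's conduct. The conclusion assumes that the programming plan adds no such tables.

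**What to change.** In SAP 6.7.2, replace the sentence that makes shift tables optional with two commitments for all cohorts, and keep the by-visit tables:
1. Baseline versus worst post-baseline CTCAE grade for each gradable parameter, using scheduled and unscheduled draws, with the number and percent newly Grade 3 or higher.
2. A count and individual listing of patients with AST or ALT > 3 x ULN and concurrent total bilirubin > 2 x ULN.

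The cost is a few extra tables and one listing from data already collected, with no new samples or visits.

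As a secondary step, clarify Protocol 7.8.1 so that Grade 3/4 laboratory findings are excepted, in agreement with 7.8.6. In practice this can affect only Cohort 4, because the pembrolizumab cohorts are closed and their treatment is complete (Protocol 2.3.1.1.2.1). It should apply to every Cohort 4 patient, including any already enrolled; otherwise AE collection would be split within a cohort of at most 15. It may need IRB/IEC approval (Protocol 11.1). The laboratory-based table gives valid counts whether or not this step is taken.

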6.7.3 Electrocardiograms

Within each patient, the values provided in triplicate at each timepoint will be averaged by the mean. These intra-patient averages will be used for calculating changes from baseline and will be used to calculate summary statistics.

For each relevant visit and timepoint, summary statistics will be calculated for the heart rate, QT interval, QT interval with Fridericia's correction (QTcF), and maximum post dose change from baseline QTcF interval (Δ QTcF).

An additional summary will display the number and percent of patients with QTcF intervals >450 msec and ≤ 450 msec at each timepoint.

An ECG data listing will display all abnormal clinical interpretations.

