5.2 Exclusion Criteria

1. Patients with symptomatic central nervous system (CNS) metastases must have been treated, be asymptomatic, and meet the following at the time of enrollment:
 - a. No concurrent treatment for the CNS disease (e.g. surgery, radiation, corticosteroids ≥ 10 mg prednisone/day or equivalent).
 - b. No progression of CNS metastases on MRI or CT for at least 14 days after last day of prior therapy for the CNS metastases.
 - c. No concurrent leptomeningeal disease or cord compression.
2. Patients with any history of known or suspected autoimmune disease with the specific exceptions of vitiligo, resolved childhood atopic dermatitis, psoriasis not requiring systemic treatment (within the past 2 years) and patients with a history of Grave's disease that are now euthyroid clinically and by laboratory testing.
3. History of prior allogeneic bone marrow, stem-cell or solid organ transplantation.
4. Treatment with any systemic anti-neoplastic therapy, or investigational therapy within the 4 weeks prior to the initiation of study drug administration.
5. Treatment with radiation therapy within 2 weeks prior to the initiation of study drug administration.
6. Treatment with corticosteroids (≥ 10 mg per day prednisone or equivalent) or other immune suppressive drugs within the 14 days prior to the initiation of study drug administration. Steroids for topical, ophthalmic, inhaled or nasal administration are allowed.
7. History of clinically significant cardiovascular disease including but not limited to:
 - a. Myocardial infarction or unstable angina within the 12 weeks prior to the initiation of study drug.
 - b. Uncontrolled hypertension: systolic blood pressure (SBP) > 180 mmHg, diastolic blood pressure (DBP) > 100 mmHg.
 - c. QTcB prolongation > 480 msec.
 - d. Congestive heart failure (New York Heart Association [NYHA] class III-IV)

8. Clinically-significant gastrointestinal disorders including:
 - a. Any history of gastrointestinal perforation unless the affected area has been deemed by the investigator to no longer be a risk for perforation by the investigator.
 - b. History of clinically significant gastrointestinal bleeding within 4 weeks prior to the initiation of study drug.
 - c. History of acute pancreatitis within 4 weeks prior to the initiation of study drug

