9.4.3 Other Safety Endpoints

ECGs will be collected and analyzed for evidence of cardiac toxicity, especially prolongation of QT interval. Vital signs will be summarized with descriptive statistics at each visit and time point where they are collected.

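### The only categorical QTcF summary, a single 450 msec cut at each time point, does not count patients with new or marked prolongation

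*SAP*

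**What the plan says.** Protocol 9.4.3 sets the purpose: "ECGs will be collected and analyzed for evidence of cardiac toxicity, especially prolongation of QT interval".

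SAP 6.7.3 averages the triplicate readings within a patient and then plans four things:

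- summary statistics by visit and time point for heart rate, QT and QTcF;
- in the same sentence, summary statistics for the "maximum post dose change from baseline QTcF interval";
- one categorical output: "An additional summary will display the number and percent of patients with QTcF intervals" above, and at or below, "450 msec at each timepoint";
- a listing: "An ECG data listing will display all abnormal clinical interpretations".

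SAP 6.1 fixes what summary statistics contain: "Continuous variables will be summarized by descriptive statistics, including the mean, standard deviation, median, minimum, and maximum". It also fixes baseline: "baseline is defined as the most recent value prior to the first infusion of any of the study drugs".

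On entry, Protocol 5.2 item 7c (repeated in the synopsis) excludes "QTcB prolongation > 480 msec". The documents give no QTcF entry limit.

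SAP 6.7.4 gives vital signs a shift table from baseline category to post-baseline category, and SAP 6.7.2 allows shift tables for laboratory values. SAP 6.7.3 gives none for QTcF.

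**The concern.** A reader of the safety results will want to know how many patients in each cohort developed a prolonged QTcF on treatment, and how many reached a high value or had a large rise. The categorical table is the natural place to look, but it cannot answer for three reasons:

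- It does not condition on baseline, although the entry criteria allow some patients to start above the cut.
- It is cross-sectional at each time point, with no worst value per patient.
- It has one cut, so a value just over 450 and one far above it are counted alike.

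Safety is a primary objective and the protocol singles out QT prolongation. Cohorts run from 3 to 20 patients, so one or two patients change the percentages visibly.

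**Working it through.** The plan gives no figure to reproduce. The check asks whether the entry limit and the table cut overlap, and what the table would then show.

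**1. Put the two limits on one scale.** The entry limit is QTcB (read here as Bazett) and the table uses QTcF (Fridericia). The standard definitions, which the documents do not write out, are QTcB = QT / RR^(1/2) and QTcF = QT / RR^(1/3), with RR = 60/HR. Hence QTcF = QTcB × (60/HR)^(1/6). For a patient exactly at QTcB 480 msec:

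| Heart rate (beats/min) | QTcF (msec) |
|---|---|
| 50 | 494.8 |
| 60 | 480.0 |
| 70 | 467.8 |
| 80 | 457.5 |
| 90 | 448.6 |
| 100 | 440.8 |

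Setting QTcF = 450 gives HR = 60 × (480/450)^6 = 88.4. Below about 88 beats/min an eligible patient can start with QTcF above 450. Below 60, QTcF can even exceed 480. Above about 88, the entry limit already keeps baseline QTcF under 450.

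**2. One pre-existing case.** In a cohort of 15 (the maximum size of an expanded escalation cohort), one patient who enters at 460 and stays there contributes 1/15 = 6.7 percentage points to the above-450 count at every time point, with no drug effect.

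**3. Share of the count that may be pre-existing.** The documents give no baseline rate of QTcF above 450, so these rates are assumptions. Let b be the proportion above 450 at baseline who stay there, and e the proportion of the rest who newly cross. The table shows b + (1 − b)e, and the pre-existing share is b / [b + (1 − b)e].

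| b | e | Shown above 450 | Pre-existing share |
|---|---|---|---|
| 2% | 2% | 4.0% | 51% |
| 2% | 5% | 6.9% | 29% |
| 5% | 2% | 6.9% | 72% |
| 5% | 5% | 9.8% | 51% |
| 10% | 2% | 11.8% | 85% |
| 10% | 5% | 14.5% | 69% |

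**4. Incidence across time points.** Protocol Table 8 schedules 14 ECG time points in Cycle 1 for the pembrolizumab cohorts: two before and two after pembrolizumab (Days 1 and 22), four before and four after MGA271 (Days 1, 8, 15 and 22), and one each at 3 and 24 hours. Thirteen of these follow the start of the first infusion. If three different patients in a cohort of 15 each cross 450 at a different time point, no cell exceeds 1/15 = 6.7%, although 3/15 = 20% were affected.

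**5. Severity.** Values of 451 and 520 fall in the same cell. A patient who moves from 455 to 520, a rise of 65 msec, leaves the table unchanged.

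**The case against.** The strongest reply is that this is one supplementary table and the rest of SAP 6.7.3 covers much of the ground:

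- Maximum post-dose change in QTcF is taken from baseline, and SAP 6.1 reports the maximum. A patient going from 455 to 520 would produce a maximum change of at least 65 and a maximum QTcF of at least 520 at that time point. A patient stable at 455 would produce neither.
- ECGs are scheduled before the first infusion, so a pre-dose row would show how many patients started above 450.
- Abnormal interpretations are listed, and QT events recorded as adverse events enter the adverse event tables.
- No escalation rule uses this table, the study is described as mainly observational, and the table shells sit in a separate programming plan that is not available here.

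All of this stands, and it rules out two stronger readings. A reader might infer that the ECG plan as a whole cannot reveal treatment-related or marked prolongation. It can, because the largest single increase and the largest value would be visible. A reader might also infer that anyone admitted near the 480 limit will count as prolonged throughout. The limit is Bazett and the table Fridericia, so above about 88 beats/min the limit itself implies a baseline QTcF below 450.

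The reply leaves the counting gap open. A maximum shows that at least one patient had a large rise, not how many. A pre-dose row compares margins but does not show who newly crossed. The listing and the adverse event tables depend on clinical interpretation and reporting, and are not threshold counts.

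**Conclusion.** The concern holds in a limited form. The single categorical QTcF output does not separate pre-existing from new values above 450, does not give per-patient incidence, and does not separate mild from marked values. No other output specified in the SAP supplies those counts.

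The overlap with the entry criteria follows from the documents' two limits and the standard correction formulas, and applies below about 88 beats/min. How often it will matter is unknown. The 29% to 85% pre-existing share rests wholly on the assumed rates, and the 6.7-point and 20% figures are illustrations in a cohort of 15.

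This is a worthwhile refinement of low priority. It affects how clearly a safety result is reported, not the escalation decisions or the conduct of the trial.

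**What to change.** Add to SAP 6.7.3, by cohort:

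- a shift table of baseline QTcF category against worst post-baseline QTcF category, one entry per patient, with categories ≤450, >450 to 480, >480 to 500 and >500 msec;
- counts of patients by maximum increase from baseline: ≤30, >30 to 60 and >60 msec.

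Use the triplicate mean as baseline, consistent with the averaging already specified, and keep the existing time-point table. The 500, 30 and 60 msec cuts are proposed for reporting and do not come from the documents. The 480 cut borrows the protocol's number but applies it to QTcF, not QTcB. None of these categories changes eligibility or patient management.

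The cost is one extra table from ECG data already collected, in the same style as the vital-sign shift tables in SAP 6.7.4.
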